## **Quantitative MRI measurements of white matter tissue structure**

**Diffusion weighted MRI (dMRI) data acquisition** – DMRI data will be acquired at 1.5 mm^3 spatial resolution (96 gradient directions, distributed across 2 b-values, b=711 and b=2855 s/mm^2). 64 diffusion directions will be sampled at the high b-value, 32 directions at the low b-value, and 8 images will be acquired without diffusion weighting (b=0). Half the b=0 images will be acquired with a reversed phase encoding direction to correct distortions due to field inhomogeneities. This sequence was determined optimal for estimation of parameters of the neurite orientation dispersion and density imaging (**NODDI**) model, based on data from a Philips Achieva scanner. The acquisition optimally balances (a) angular resolution/contrast to estimate fiber orientation distribution functions for tractography, (b) multiple shells to estimate tissue properties based on multiple compartment models and (c) signal to noise ratio (SNR) given the time constraints of working with children.

**Fiber tractography** – Fiber orientation distribution functions will be estimated using constrained spherical deconvolution (CSD) as implemented in the Diffusion in Python (DIPY) software package. Optimal parameters for model fitting will be determined based on cross-validation. Fibers will be estimated using probabilistic tractography. Given concerns over false positives in tractography (erroneous fibers) highlighted by us and others, the Linear Fascicle Evaluation (LiFE) algorithm will be used to control for false positives, and retain an optimized set of fibers. Fascicles will then be identified within each individual's brain using the AFQ software package, and analyzed in relation to reading skills over the course of the intervention. AFQ measurements are highly reliable ( $r = 0.93^6$ ) and are, therefore, well suited for longitudinal studies.

**Modeling tissue structure from dMRI measurements** – The diffusion of water molecules probes the microscopic structure of brain tissue. Membranes create obstacles to the diffusion process, leading to declines in the rate of diffusion, and creating separate compartments of intra- and extra-cellular water that can be distinguished with dMRI. The multi-b-value, dMRI sequence of the proposed study will make it possible to estimate the proportion of water that is restricted within cell bodies and axons (neurites), adding an additional layer of specificity to our biological interpretation. Mean diffusivity (**MD**) and fractional anisotropy (**FA**) will be computed to characterize Gaussian diffusion and intracellular water volume fraction (based on the NODDI model) will be calculated to characterize changes in the amount of water that is contained within cellular structures. Intracellular volume fraction will change if axons grow larger in diameter in during learning.

**T1 and MTV mapping** – Our goal is to go beyond simply localizing learning-induced changes and work towards understanding the neurobiology of these changes. Diffusion measurements will be combined with quantitative MRI measurements of T1 relaxation rate and macromolecular tissue volume (**MTV**, introduced by Mezer, [name] and colleagues). T1 measures of the longitudinal relaxation rate of hydrogen protons in a magnetic field and post mortem work has demonstrated that, in white matter, T1 is primarily driven by variation in myelin content. The PI and collaborators have confirmed that qMRI measures of MTV are an accurate index of the true volume of tissue macromolecules within each voxel. Thus, MTV can be used to directly monitor the creation of new tissue over the course of an intervention and, in combination with T1, can be used to make inferences as to the cellular composition (e.g., myelination) of tissue at millimeter resolution. Quantitative T1 and MTV mapping will be performed by collecting T1-weighted images (SPGRs) at multiple flip angles (1mm^3 resolution) and transmit coil inhomogeneity (B1) will be corrected based on unbiased T1 estimates from a low resolution spin-echo inversion recovery sequence. T1 and MTV values will be mapped to fiber tracts using AFQ.

[figure not shown]
**Combining qMRI and dMRI for a more accurate model of human brain tissue:** The qMRI and dMRI measurements in **Aim 1** are independent acquisitions and we have demonstrated in previous work that these measures are sensitive to independent biological processes in the white matter. These measures provide a means to differentiate changes in intracellular water fraction from changes in myelin. For example, although the branching of astrocyte processes has a large impact on diffusion, astrocytes are believed to have a smaller impact on T1 relaxation than do changes in myelin. Given that we have confirmed that measures of T1 and diffusion have similar SNR^4, and similar sensitivity to developmental change, the presence of common versus differential effects in the two modalities would point to distinct biological underpinnings. An interpretation of differential effects in the two measures will have to acknowledge and account for differential biases (e.g., subject motion introduces bias into diffusion, but not qMRI measures ), but **such a finding would be novel in the literature**. In summary, combining multiple MRI techniques will lead to a more detailed description of underlying biological sources of white matter plasticity during learning and build new bridges with animal models.

## Research questions and preliminary data

**Aim 1.A: Does intervention cause short-term, transient changes in the white matter, or long-term remodeling of the brain circuit?** Based on previous work, we find highly significant changes ( $p < 0.0001$ ) in diffusion properties for an extensive network of white matter tracts (Figure 2 A,B,C), and stability in a control group. Surprisingly, even tracts beyond the core reading circuitry show dramatic learning-induced plasticity. Hence, there is no question that reading intervention causes rapid and widespread changes in white matter tissue properties. However, there are many potential interpretations for these changes that point to different underlying mechanisms. For example, we might interpret changes in mean diffusivity as reflecting increased “white matter integrity”, and infer that white matter deficits in children with dyslexia are remediated by the intervention program^80. Alternatively, we might posit that the changes in mean diffusivity reflect transient changes in oligodendrocyte precursor cells (and other glial cells) resulting from the new experience of the intervention, but not reflecting permanent remodeling of the brain circuit. Under this second interpretation, white matter plasticity is still critical to the learning process (in line with animal work), but reflects a more nuanced mechanism than typically considered in human studies. To dissociate these alternative accounts of experience-dependent plasticity and dyslexia-remediation, we will analyze follow-up measurements at 6 and 12 months post-intervention to determine if: (a) diffusion properties return to baseline, (b) changes remain stable or continue to grow over time, or (c) diffusion properties remain stable or continue to grow **only in tracts that are critical for skilled reading** (e.g., left arcuate fasciculus and ILF), but return to baseline in other tracts (Figure 2D).

These data will offer a new understanding of white matter plasticity and learning by either: (1) confirming the stability of rapid, learning-induced changes, or (2) dissociating short-term and long-term mechanisms of change. **No study has examined the relationship between short-term and long-term mechanisms of plasticity**, meaning that findings will be novel, irrespective of how the results

**Figure 2: Diffusion measurements detect highly significant, intervention-driven white matter plasticity.** LME models were used to model changes in mean diffusivity as a function of hours in the intervention (change/hr). (A,B) Significant linear growth was detected in a network of tracts including, but not limited to, the “core reading circuitry”. Linear growth rates are shown for each tract, color-coded based on the p-value from the model. There is an extensive literature linking a core network of tracts (including the left arcuate fasciculus and left ILF) to reading skills. Surprisingly, our data demonstrate rapid, intervention-driven changes in these tracts, as well as many other tracts that are not conventionally associated with reading. Based on a simulation conducted with these data, the proposed sample size has excellent power to reliably measure white matter plasticity: assuming a 10% attrition rate, which is larger than the attrition in the pilot study, power = 0.98 for the left arcuate and 0.95 for the left ILF at  $\alpha = 0.05$ . (C) Mean diffusivity sampled along the trajectory of the ILF (from the occipital pole to the temporal pole) shows incremental growth between each measurement session, and along the full tract. Error bars represent  $\pm 1$  SEM. Over the course of learning, many tracts show very similar growth trajectories to the one displayed for the ILF. (D) Why does such an extensive network show highly significant changes during the intervention? One hypothesis is that the structural changes seen during the intervention are transient and will return to baseline when the intervention is complete. Alternatively, we might hypothesize that only the tracts that are critical for maintaining the behavioral improvements, tracts that are considered to be the “core circuitry for reading”, will show sustained change or continued growth after the intervention is complete. This hypothesis is illustrated in panel D. During the baseline period we expect stability in the measurements: **19 control subjects not enrolled in the intervention showed no change over the course of 4 measurement sessions**. Hence, changes are not attributable to development or repeated scanning. During the intervention period we observe plasticity in the core reading circuitry (orange) and other, non-core tracts (blue). At 6-month and 12-month follow up sessions, our “transient change hypothesis” predicts that many of the measures will return to baseline and match the dyslexic control group. Critical tracts that support the behavior are predicted to show continued growth, and this growth will also be reflected in changes in quantitative T1 and MTV values (see Aim 1.B).

turn out. Given the high power for detecting short term learning effects (power = 0.95-0.99 at  $\alpha=0.05$ ), **Aim 1.A** is a low-risk, high-reward endeavor.

**Aim 1.B: Do different properties of the white matter display different time-courses of plasticity?** We measured rapid changes in mean diffusivity that emerge within just a few weeks of intervention (**Figure 2C**). This is in line with studies reporting mean diffusivity changes after hours of learning, and animal models indicate that these rapid changes are likely to reflect the morphology of glial cells. However, we cannot determine from diffusion measurements alone if changes in the diffusion signal are driven by glia (as suggested in the aforementioned work), or if there are also changes in myelination and axon properties, as we might expect from recent animal work demonstrating that myelin plasticity is a critical component of learning. By collecting long-term follow up measurements, and combining new, cutting-edge quantitative MRI pulse sequences and biophysical models, we will be able to better understand the underlying biology and time-course of the rapid white matter plasticity. We hypothesize that our data will fall in line with the sequence of changes that occur in mouse models of learning: initial proliferation of glial cells throughout an extensive network, followed by long term remodeling of axons and myelin within the specific pathways that are critical for the behavior. The initial proliferation of glial cells would have a dramatic impact on mean diffusivity, but limited impact on T1, or MTV values. Subsequent changes in myelin would have a dramatic impact on T1 and MTV values, but limited impact on m diffusivity. Though no MRI measure is specific to a single tissue type, combining multiple measures makes it possible to reason about the most likely biological source.

**Aim 1.C: Does white matter plasticity track behavioral improvements?** Seminal work by Barres and colleagues demonstrated that electrical activity on an axon causes oligodendrocytes to respond with increased wraps of myelin. This work inspired a surge of interest in understanding the role of white matter plasticity in learning. But an outstanding question is the extent to which changes in the white matter reflect the process of remodeling the circuit to support changes in behavior, versus simply experience dependent changes that do not directly relate to learning of the new behavior. Recent work published in *Science*, demonstrated that activity-dependent changes in myelin are fundamental for motor learning in a rodent model. When receptors on oligodendrocytes were blocked, meaning that myelination remains constant but no new myelin is created in response to electrical signals, mice did not learn a complex motor task. While this work clearly demonstrates that myelin is critical for learning, **it does not indicate that all changes in the white matter are important for learning**. For example, one interpretation of our pilot data is that the new experiences associated with the intervention program promote cellular changes that are not tightly linked to behavioral improvements.

**Aim 1.C** will investigate the link between white matter plasticity and behavior. Three statistical approaches will be employed. First, LME models will be used to test whether changes in diffusion properties, MTV and T1 track behavioral changes during the intervention. To limit the number of statistical comparisons, we will perform a principal component analysis (PCA) of the reading scores and use the first PC as a general index of reading abilities. For any significant effect, we will conduct post-hoc analyses to determine if it is specific to certain measures of reading skills. Pilot data show a statistically significant, but modest, relationship between the time-course of MD change within a subject and improvements in reading score ( $r = -0.30$  Arcuate,  $p = 0.003$ ;  $r = -0.32$  ILF,  $p = 0.006$ ). Second, correlation analysis will be used to analyze whether changes in white matter tissue properties between: (a) the baseline period and the long-term follow-up sessions and (b) the immediate post-intervention session and the long-term follow-up sessions, correlate with individual differences in the amount of behavioral change. We hypothesize that the rapid changes in diffusion properties observed during the intervention are experience-dependent but do not reflect learning per se, and will only show a modest relationship to individual differences in learning. Instead it will be the longer-term changes in T1 values (indicative of myelination) that predict crystallized skill acquisition. Third, we will perform an **exploratory analysis** using latent change score modeling to investigate whether the data support time-lagged relationships between growth in the white matter and growth in reading skills.

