**Control subjects:** Multiple baseline measurements in each intervention subject will be used to establish the stability of our measurements, and control for the effects of repeated testing over the intervention period. Additionally, **two control groups** will be recruited to assess long-term change in the absence of intervention. Each control group will include 20 subjects **matched in terms of age, gender, non-verbal IQ and socioeconomic status**. One control group will also be matched in terms of reading skills (**dyslexic control**) and will serve as a comparison for post-intervention changes in children with dyslexia. The other control group will consist of typical readers and will serve as a comparison for typical development. Based on the typical-reading control group, we can assess neural differences in the subjects with dyslexia and examine “normalization” of deficits associated with dyslexia. Control groups will participate in four measurements sessions: (1) a baseline session followed by longitudinal visits at (2) two months (length of intervention), (3) eight months and (4) 14 months. Dyslexic control subjects will be offered the opportunity to participate as intervention subjects the following summer.

**Statistics:** Longitudinal change will be modeled with linear mixed effects (LME) models. LME models are preferable to repeated measures ANOVAs for two reasons: (1) subjects with missing data points do not need to be excluded; (2) non-linear effects can be modeled by adding higher-order polynomials terms. Model selection based on Bayesian information criteria will be used to determine the random effects structure.

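### Aim 1.C's contrast of rapid diffusion change with long-term T1 change varies measure, window and method together and ignores error in change, so a weaker MD link does not by itself show weaker coupling to learning

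*Combined protocol and SAP*

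**What the plan says.** Aim 1.C (Aim 1, Research questions and preliminary data) sets out three approaches.

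- During the intervention: "LME models will be used to test whether changes in diffusion properties, MTV and T1 track behavioral changes during the intervention".
- Over longer windows: "correlation analysis will be used to analyze whether changes in white matter tissue properties between" two pairs of time points, namely (a) the baseline period and long-term follow-up, and (b) "the immediate post-intervention session and the long-term follow-up sessions, correlate with individual differences in the amount of behavioral change".
- Latent change score modelling, labelled exploratory and directed at time-lagged relations.

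The hypothesis is that the rapid diffusion changes "will only show a modest relationship to individual differences in learning. Instead it will be the longer-term changes in T1 values" that predict consolidated skill. A weak MD link therefore counts in the hypothesis's favour.

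On measurement quality, the Fiber tractography paragraph describes AFQ measurements as highly reliable (r = 0.93) "and are, therefore, well suited for longitudinal studies". The paragraph on combining qMRI and dMRI adds that "we have confirmed that measures of T1 and diffusion have similar SNR", and that an interpretation of differential effects must account for differential biases, with motion as the example. Under Control subjects, the repeated baseline scans "will be used to establish the stability of our measurements". Aim 1.C does not say that this information enters the association analyses.

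**The concern.** The hypothesis is a comparison: MD over a short window against T1 over a long one. As planned, the two sides come from different measures, windows and statistical methods, and nothing in Aim 1.C compares them directly.

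Both methods are sensitive to error in the imaging measure. A correlation of observed change is shrunk by the square root of the reliability of change. A mixed-model slope is diluted when the error-prone MD value is the predictor. A reliability of 0.93 for a tract measurement does not fix the reliability of a child's change. That depends on how much true change differs between children over the window, and the documents do not report it. Similar SNR for T1 and diffusion describes the measures, not their change over these windows.

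At stake is the conclusion that rapid diffusion change reflects experience but not learning, while T1 change carries learning. If the two links are diluted by different amounts, their observed sizes do not rank the underlying coupling.

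**Working it through.** **The plan's own figure.** Aim 1.C reports a pilot "relationship between the time-course of MD change within a subject and improvements in reading score" of r = −0.30 (p = 0.003) for the arcuate and r = −0.32 (p = 0.006) for the ILF. With t = r√df/√(1 − r²), r = −0.30 gives p = 0.14 for 26 children and p = 0.002 for 26 × 4 = 104 scans; p = 0.003 needs n of 93–99. For r = −0.32 the values are 0.11 and 0.0009, and p = 0.006 needs n of 72–73. Neither the n nor the model behind these p-values is stated, so whether they reproduce cannot be judged. The point below does not depend on them. They also describe a within-child time course, so they are not comparable with the between-child correlations below.

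**Inputs for the illustration.**
- Reliability 0.93 (Fiber tractography). The documents do not say what this r measures and give no separate T1 value. I take it as between-child reliability of levels and apply it to both measures.
- 40 intervention children with 10% attrition, so 40 × 0.9 = 36 (Statistical Design and Power).
- Assumed: true correlation of 0.5 between brain change and reading gain for both measures; reading gain without error; one scan at each end of a window; SD of true change, s, of 0.2 to 0.6 in units of the between-child SD of levels.

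**Change scores.** Error variance of a difference is 2 × (1 − 0.93) = 0.14. Reliability of change is s²/(s² + 0.14), and the expected correlation is 0.5 × √reliability. For s = 0.3: 0.09/0.23 = 0.39, and 0.5 × √0.39 = 0.31. For s = 0.6: 0.36/0.50 = 0.72, and 0.5 × √0.72 = 0.42.

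| s, short (MD) | s, long (T1) | Reliability, short | Reliability, long | Expected r, MD | Expected r, T1 |
|---|---|---|---|---|---|
| 0.3 | 0.6 | 0.39 | 0.72 | 0.31 | 0.42 |
| 0.2 | 0.6 | 0.22 | 0.72 | 0.24 | 0.42 |
| 0.3 | 0.3 | 0.39 | 0.39 | 0.31 | 0.31 |
| 0.6 | 0.3 | 0.72 | 0.39 | 0.42 | 0.31 |

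A simulation at 36 children (40,000 replicates) gave mean correlations within 0.01 of every row. True coupling is identical throughout, and only the spread of true change moves the observed values.

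**Mixed model.** The short window is not a change-score correlation, so the MD column shows the mechanism and is not a forecast. The mixed model is not immune, however. Suppose reading is regressed on observed MD within child over two baseline, one mid-point and one post-intervention scan, with linear true change (0, 0, 0.5, 1 times the child's change) and no group-average change. The squared deviations of these four values from their mean of 0.375 sum to 0.6875. The fraction of the slope retained is 0.6875s²/(0.6875s² + 3 × 0.07). For s = 0.3 this is 0.062/0.272 = 0.23; for s = 0.6 it is 0.248/0.458 = 0.54. A group-average change left in the MD predictor would lessen the dilution. If MD is the outcome instead, its error widens the interval but does not bias the slope. The plan does not say which variable is the predictor.

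**The case against.** A reader might infer that scan error alone produces the predicted pattern, always in favour of the hypothesis. The documents do not support that. With equal scan error and equal numbers of scans, a gap appears only if the spread of true change differs, and no spread is given for either window. Aim 1.B expects a large early effect on diffusivity and later effects on T1 and MTV, and Aim 1.A allows diffusion changes to return to baseline. Spread over the intervention could therefore be as large for MD as it is for T1 later, or larger. The last two rows of the table show no gap and a reversed gap.

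A reader might also infer that the 8-week MD link is itself a raw change-score correlation. It is not: that window is assigned to mixed models, and the correlations cover only windows ending at follow-up.

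It can fairly be added that much of the raw material for a remedy is already planned. The mixed models cover diffusion, MTV and T1 alike, and the correlations cover tissue properties in general, so same-window results for both measures will exist. Latent change modelling is included, the baseline scans serve to check stability, and the plan acknowledges differential bias.

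These objections remove any claim about direction. They do not close the gap. No window-matched comparison is specified, the latent change model is exploratory and aimed at time lags, and the acknowledged bias is motion, not the reliability of change.

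**Conclusion.** The point holds as a limit on interpretation. Aim 1.C cannot distinguish weaker coupling of rapid MD change from greater dilution of its estimate, because it plans neither a direct comparison with T1 nor any allowance for error in change.

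The size is undetermined from the documents. Under the stated assumptions, equal coupling gives differences in expected correlation (T1 minus MD) from 0.19 in favour of the hypothesis (0.42 against 0.24 before rounding) through zero to 0.11 against it. These figures rest on applying 0.93 to both measures, a true correlation of 0.5 and assumed SDs of true change. They show that the observed contrast is uninformative without the missing quantities; they do not predict what the trial will find.

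**What to change.** 1. Estimate each measure's within-child error and reliability of change from the two baseline scans and the control-group sessions. Report these in the Fiber tractography paragraph and in Aim 1.C in place of relying on r = 0.93.
2. Estimate the MD–reading and T1–reading links in the same windows (during the intervention, baseline to follow-up, and post-intervention to follow-up). Use one model that separates child-level change from session error, for example a bivariate mixed or latent change model. Test the difference between the two dependent associations and give its confidence interval. State which variable is the predictor.
3. Conclude that rapid diffusion change does not reflect learning while T1 change does only if that window-matched, error-adjusted difference supports it.

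The change is to analysis wording and modelling, and all the scans are already planned. The cost is precision. At 36 children an observed correlation of zero has an upper 95% limit of tanh(1.96/√33) = 0.33. Dividing by √0.39 = 0.63 (s = 0.3, reliability treated as known) raises it to about 0.53. For that reason I would not add a rule that calls the MD link modest only when its upper limit falls below a fixed value; at this sample size it could rarely be met.

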## **Statistical Design and Power**

**Aim 1:** Aim 1 targets the relationship between white matter plasticity and learning and seeks to quantify changes in the white matter that occur with intervention. There will be 40 intervention subjects and 40 control subjects. Linear mixed effects models will be used to compare white matter changes during the intervention period to (a) the control period and (b) the control group. Simulations based on pilot data in 26 subjects indicate exceptional statistical power: 0.98 for the arcuate fasciculus (primary tract of interest) and 0.95 for the inferior longitudinal fasciculus (secondary tract of interest) at  $\alpha=0.05$ . This power analysis takes into account an expected 10% attrition rate. In the pilot study there was no subject attrition. Additional details are provided on page 6 (see Figure 2 caption) of the Research Strategy.

**Aim 2:** Aim 2 targets changes in the computations performed by the visual word form area, a region that is critical for rapid and automatic word recognition. Functional magnetic resonance imaging data will be used to measure the selectivity for words compared to other stimuli in this region. This aim uses the same subjects as Aim 1. Linear mixed effects models will be used to compare white matter changes during the intervention period to (a) the control period and (b) the control group. Based on pilot data, a power analysis confirms excellent statistical power: mean % BOLD increase = 0.15, SD = 0.034, bias corrected SD = 0.036, power  $> 0.95$  at  $\alpha=0.05$ . Additional details are provided on page 10 of the Research Strategy.

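### Aim 1.C hypothesises that longer-term T1 change, rather than rapid diffusion change, predicts lasting reading skill, but no planned analysis is described as testing the difference between the two associations

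*Combined protocol and SAP*

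**What the plan says.** Aim 1.C (under Research questions and preliminary data) lists three approaches.

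- Mixed models: "LME models will be used to test whether changes in diffusion properties, MTV and T1 track behavioral changes during the intervention". Reading is summarised by the first principal component of the reading scores.
- Individual differences: "correlation analysis will be used to analyze whether changes in white matter tissue properties between" two pairs of time points, namely baseline to long-term follow-up and immediate post-intervention to long-term follow-up, relate to the amount of behavioural change.
- An exploratory latent change score model, "to investigate whether the data support time-lagged relationships between growth in the white matter and growth in reading skills".

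The hypothesis has two halves. Rapid diffusion change during the intervention "will only show a modest relationship to individual differences in learning". The second half begins with a contrast: "Instead it will be the longer-term changes in T1 values (indicative of myelination) that predict crystallized skill acquisition".

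The subsection on combining qMRI and dMRI (under Quantitative MRI measurements of white matter tissue structure) says how such a pattern would be read: "the presence of common versus differential effects in the two modalities would point to distinct biological underpinnings". It asks that differential biases be accounted for, but names no test of whether effects differ. Statistical Design and Power adds, for Aim 1, only mixed-model comparisons with the control period and the control group.

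**The concern.** The diffusion relationship is expected to be modest, not absent. A clear T1 correlation on its own therefore does not confirm the hypothesis, and neither does a T1 correlation below p = 0.05 beside an MD correlation above it. The quantity that bears on the hypothesis is the difference between the two associations, and nothing in the plan is described as estimating it.

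The two halves also sit on different time windows and use different words for the outcome (learning in one, crystallised skill in the other). As written, the diffusion half could be judged from the intervention-period mixed model and the T1 half from the follow-up correlations. The two results would then stand side by side without a formal comparison. At stake is a mechanistic conclusion, that myelin-related change matters more for lasting skill than early diffusion change, which could be drawn when the two associations are the same size.

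**Working it through.** The plan gives no sample size, power or effect size for a T1-versus-diffusion comparison, so there is no figure of its own to reproduce.

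**Inputs from the documents.**
- Sample: "There will be 40 intervention subjects and 40 control subjects". Individual differences in response concern the 40 intervention children.
- Attrition: "This power analysis takes into account an expected 10% attrition rate". 40 × 0.90 = 36.
- Alpha is 0.05; sidedness is not stated, and two-sided is assumed.
- Pilot MD-reading association (Aim 1.C): r = −0.30 for the arcuate and −0.32 for the ILF. These are within-subject time-course values, so they are only a rough guide to a between-child correlation.

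**Assumptions.** Both associations are simple correlations with one reading outcome, signs aligned so that positive means the expected direction. True values are 0.3 to 0.4 when equal. The T1-MD change correlation, c, is 0 to 0.5.

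**Step 1: significance threshold.** Critical r = t/√(n − 2 + t²), with t(0.975, 34) = 2.032. This gives 2.032/√(34 + 4.130) = 0.329, close to the pilot MD values.

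**Step 2: power of one correlation.** Using Fisher z, atanh(0.30) × √33 = 0.3095 × 5.745 = 1.778, and Φ(1.778 − 1.960) = 0.43. Each correlation is nearly a coin toss. Treated as independent, the chance that T1 is significant and MD is not is 0.43 × 0.57 ≈ 0.245.

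**Step 3: simulation with equal true correlations, n = 36** (40,000 samples per setting).

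| True r (both) | c | T1 significant, MD not | Direct test rejects (two-sided) |
|---|---|---|---|
| 0.3 | 0 | 25% | 5% |
| 0.3 | 0.3 | 21% | 5% |
| 0.3 | 0.5 | 17% | 5% |
| 0.4 | 0 | 22% | 5% |
| 0.4 | 0.3 | 19% | 5% |
| 0.4 | 0.5 | 15% | 5% |

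Among the samples in which only T1 is significant, the direct test supports a difference in about 10 to 12%. With all 40 children the pattern is similar: 25% and 22% for r = 0.3 at c = 0 and 0.3, and 20% and 17% for r = 0.4.

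**Step 4: the direct test.** Williams' t for two correlations sharing one variable is t = (r₁ − r₂) √{(n − 1)(1 + c) / [2((n − 1)/(n − 3))D + r̄²(1 − c)³]}, where D = 1 − r₁² − r₂² − c² + 2r₁r₂c, r̄ is the mean of r₁ and r₂, and there are n − 3 degrees of freedom.

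Worked example, n = 36: observed T1 r = 0.40 (p = 0.016), MD r = 0.30 (p = 0.076), c = 0.3. D = 1 − 0.16 − 0.09 − 0.09 + 0.072 = 0.732. Then t = 0.10 × √[45.5/(1.553 + 0.042)] = 0.10 × 5.34 = 0.53, p = 0.60. At c = 0 and 0.5 the p values are 0.65 and 0.53. One correlation is significant and the other is not, with no evidence that they differ.

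**Step 5: power of the direct test, n = 36.**

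| True T1 v MD | c = 0 | c = 0.3 | c = 0.5 |
|---|---|---|---|
| 0.5 v 0.1 | 44% | 58% | 74% |
| 0.6 v 0.1 | 67% | 83% | 94% |
| 0.5 v 0.3 | 15% | 19% | 26% |

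For 80% power at 0.5 v 0.3, about 300 children are needed at c = 0, 220 at c = 0.3 and 130 at c = 0.6.

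**The case against.** The strongest reply is that the plan contains no rule of the kind simulated. A reader might infer that the trial will declare a dissociation whenever T1 passes p < 0.05 and MD fails. The documents do not say so. The sentence is a hypothesis, the authors already call a statistically significant pilot MD association modest, and modest describes size, not failure to reach significance. Nor may one infer that only separate correlations are planned: mixed models and an exploratory latent change model are there too. These corrections stand. What remains is that none of the three analyses is described as contrasting T1 with diffusion, while the hypothesis is that contrast.

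A second reply is that two correlations over one window with one outcome are a simplification. The hypothesis sets diffusion change during the intervention against T1 change over the longer term. This also stands, and it has two consequences: the percentages are conditional on that simplification, and a fix that forced both measures into one window would discard the rapid-versus-longer-term question. A difference test does not need the same window; it needs the same children and the same outcome.

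Third, Aim 1.B concedes that no MRI measure is specific to one tissue type, and the Aim 1 Alternative strategies promise checks under other modelling frameworks. This tempers interpretation but does not compare the two associations.

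**Conclusion.** The point holds in a limited form. Aim 1.C states a comparative hypothesis, and no planned analysis is described as testing the comparison. If the two associations were judged one at a time, equal true correlations of 0.3 to 0.4 would give a T1-only pattern in about 15 to 25% of trials at n = 36. This rests on simple correlations with one shared reading outcome, two-sided alpha of 0.05, and a T1-MD change correlation of 0 to 0.5. The documents supply no T1-behaviour correlation, so all of these values are assumed.

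A reader might go further and count every discordant result, in either direction, which roughly doubles the rate (31 to 51%). Only the T1-significant, MD-not direction would favour the stated hypothesis, so the smaller range is the relevant one. Nor does the point reach the Aim 1 comparisons of intervention-period change with the control period and control group. It concerns one mechanistic hypothesis within a sub-aim and is worth fixing because the repair is cheap.

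**What to change.** Keep the three Aim 1.C analyses and add one prespecified comparison: the difference between the T1-change and MD-change associations with reading, with a 95% confidence interval, from a Williams or Steiger test or a bootstrap over children.

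- Use the arcuate, the same children, and the same reading index (the first principal component) for both associations.
- Keep the hypothesised windows: diffusion change during the intervention and T1 change to long-term follow-up. Name the follow-up session and the reading-change interval in advance.
- Repeat the comparison with both measures over one window as a sensitivity analysis.
- State the expected sign of each association beforehand, so that strengths are compared in the same direction.
- Claim a T1-over-diffusion dissociation only if the interval excludes zero; otherwise report the two associations without ranking them.

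No new data are needed. The cost is a harder claim: at n = 36, power is about 44 to 74% for 0.5 v 0.1 and 67 to 94% for 0.6 v 0.1. It is only 15% to about a quarter for 0.5 v 0.3, which would be the relevant case if the between-child MD correlation were near the pilot's within-subject 0.30. The plan should say so in advance, so that an interval that includes zero is not read as evidence that the associations are equal.
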